#### *1.7.2.5 Duration of Treatment*

This study is designed to evaluate the safety and tolerability profile of ALK-001 in subjects over 60, and to determine the efficacy of ALK-001 on the progression of geographic atrophy.

The initial treatment period will end when the last subject completes the last scheduled visit.

A 2-year open label extension is planned to explore chronic maintenance dosing, as well as long term efficacy in case 2 years would not be sufficient to show an effect. Subjects who complete the initial treatment period may be offered to continue treatment, with a possible interruption between the first 2 years of treatment and the open label extension. Details of the extension period may be provided in future protocol amendments.

#### *1.7.2.6 Study Control, Randomization and Masking*

To prevent or reduce bias, a placebo will be used. This is particularly important as endpoints such as best-corrected visual acuity, measurement by the study team or reading center of RPE lesion atrophy, or microperimetry testing can be influenced with bias. Placebo will also be used to assess safety and establish the type, severity and frequency of adverse events associated with the drug.

Treatment masking will be in place to further reduce bias during data collection and analysis. Randomization will ensure there is no bias in the assignment of subjects to treatment groups, and to enhance the validity of statistical comparisons across treatment groups. No stratification will be used.

Investigators and clinical staff, subjects and all sponsor personnel having contact with the study sites will remain masked to the treatment allocation for the duration of the study. The labels on the packaging of the study drug only indicate a random medication number (eg: "CA27") and not the actual treatment assignment. All capsules weigh, look, smell and taste the same.

Unmasking of certain personnel when necessary for some data analyses, will require sponsor's approval and will be clearly documented.

#### *1.7.2.7 Safety Evaluations*

Based upon vitamin A's known safety and tolerability profile, possible AEs of interest have been identified and will be monitored during this study (see section 1.5.8.1). Safety data will be acquired by: 12-lead ECG, physical exam, ocular exams, clinical laboratory values, BCVA, OCT, FA, OCTA, and FAF.

To make sure that any potential for hypervitaminosis A is detected, adverse reactions such as headaches, nausea, dry lips, dry skin, signs such as papilledema (optic disc swelling), and clinically meaningful changes in clinical laboratories will be explored. Any clinically significant level will be reported as an AE (see section 1.16.1.4). In addition, levels of retinol, retinoic acid, and retinyl esters will be measured periodically. In order to avoid study unmasking, such data will be reviewed by the SMC. See section below on pharmacokinetic evaluations.

Vitamin A-related adverse reactions are usually reversible upon discontinuation of the vitamin.

#### *1.7.2.8 Pharmacokinetic Evaluations*

Plasma will be collected to measure compliance and further assess the pharmacokinetic profile of ALK-001, how it might be influenced by dietary vitamin A intake, how it fluctuates over a 2-year period as liver stores are turned over, and how the percentage of deuterated vitamin A in the blood might be linked to the progression of GA.

Metabolites of vitamin A measured in this study: ALK-001 is expected to replace existing, non-deuterated vitamin A. Total vitamin A in the plasma will be approximated by the sum of retinol + retinyl palmitate. Deuterated retinyl palmitate peaks 4-hours post ALK-001 dose then rapidly returns to levels close to baseline levels 24 hours post-dosing. Deuterated retinol increases more slowly to peak 8-12 hours following dosing and decreases more slowly over time. Retinoic acid, another vitamin A metabolite, with direct function on vision, will be measured. The absolute levels

and percentage deuteration of retinol, retinyl palmitate and retinoic acid will be measured. Percentages are calculated as the ratio between the deuterated analyte and the total amount of each analyte. Total amounts of each analyte will be calculated as the sum of the deuterated and the non-deuterated analyte. Absolute levels above the upper limit of normal may not indicate toxicity in the absence of clinical signs or other clinically meaningful laboratory abnormalities.

In this trial, levels of each analyte are expected to remain within the following ranges, considered normal based on a review of the literature:

Analyte (total deuterated + non-deuterated)	Approximate upper limit of normal
Retinol	1,500 ng/mL
Retinyl palmitate (random)	5,000 ng/mL
Retinyl palmitate (12+ hour after dosing)	500 ng/mL
Retinyl palmitate (24+ hour after dosing)	200 ng/mL
Retinoic acid (random)	5 ng/mL

#### 1.7.2.9 Efficacy Evaluations

Effects of ALK-001 on the progression of GA will be evaluated using fundus autofluorescence imaging. Although atrophic lesions can be readily measured using FAF imaging, OCT imaging will be used to confirm that the measured areas are indeed atrophic regions of the retina.

In addition, other measures of efficacy will be explored, by measuring the following variables:

- Incidence of CNV,
- BCVA,
- Reading speed,
- Visual questionnaires,
- Microperimetry (wherever available).

#### 1.7.2.10 Complement and Genotype

We propose to explore the association between each subject's response to ALK-001 and their complement status, as determined by *genetic polymorphisms (SNPs)*, *serum levels*, and *complement function* (synonym of “*activity*”). We are interested in complement because vitamin A dimers are known to activate the complement cascade [20, 30]. We have also shown that inhibiting dimerization in mouse leads to normalization of the transcription of genes involved in the complement [85].

The complement system comprises approximately 20 proteins synthesized by the liver and the RPE [86]. AMD risk is strongly associated with DNA variants for the genes encoding for complement system proteins. For example, complement factor H (CFH) itself is strongly associated with AMD [53-56], with a single common variant explaining ~43% of AMD risk in older adults. Common genetic variants in complement component C3, Factor B, C2, and Factor I also confer a risk for the disease [87]. In contrast, certain mutations spanning CFH, confer protection from developing AMD [88, 89]. Genetic testing can give information about the risk of developing AMD, but to date there have been no solid associations between genetic mutations and severity of geographic atrophy progression, or response to therapeutic intervention [90-92]. To

address this shortcoming, this study will carry out genetic testing and quantification of serum complement proteins, and in addition, test the actual function (see table below) of the complement system in each patient, as genetic variants may result in differences in complement function even in absence of gene expression differences. As complement function is constant over time [93, 94], and complement is expected to function similarly in the retina, complement function in the plasma will be measured using the commercial CH50 and AH50 tests.

We suspect that vitamin A dimers, which form on the surface of the phospholipids of the disk membranes, modify disk membranes in ways that activate complement. Such complement activation caused by vitamin A dimer-modified disk membranes would explain data linking vitamin A dimers to complement. Such a scenario would also predict that patients whose complement system reacts more strongly to dimers-altered disk membranes, would most benefit from preventing such alteration through administration of ALK-001. We thus plan to evaluate complement status as a means to predict the extent to which patients may benefit from ALK-001. We will search for a correlation between complement serum levels and/or genetic polymorphisms of approximately 20 AMD-associated genes, and/or, complement function with treatment effects as measured GA growth rates.

Accordingly, we will collect serum samples from participants and test:

**(1)** Complement function will be measured using two commercial assays:

Test Name	Notes	Range	Ref.
Complement, Total, function (CH50)	Measures the ability of the membrane attack complex to form and lyse altered liposomes decorated with foreign dinitrophenyl groups.	30-75 U/mL	[95]
Complement, Alternate (AH50)	Activates serum then quantifies formation of the C5b-9, membrane attack complex, via the alternative pathway	>46%	[96]

**(2)** Complement serum levels of C3d, Ba, C3a, C5a, SC5b-9, C3, C4, factor B, factor H and factor D will be quantified.

**(3)** Complement genetic polymorphisms (SNPs) of 20 genes associated with AMD will be tested by Fulgent Diagnostics, a CLIA certified lab. The genes include: ABCA4, C2, C3, CFB, CFH, CFI, CNGB3, CST3, CX3CR1, EFEMP1, ELOVL4, ERCC6, FBLN5, HMCN1, HTTRA1, PRPH2, RAX2, RLBP1, RPGR, TLR4, which are all part of the standard Fulgent “AMD panel”, as well as ARMS2 individually. Additional genes may be added to this list.

We will compare 1) Complement function; 2) Complement serum levels and 3) Complement genetic polymorphisms (SNPs) with rates of GA growth as determined by FAF, in order to determine the extent to which any of these variables is predictive of which AMD patients will benefit most from ALK-001.

#### 1.7.2.11 Avoidance of vitamin A supplements and liver products during the trial

Because ALK-001 is used to replace vitamin A, any overly high intake of dietary vitamin A will reduce the activity of the drug. Study participants should avoid taking items that are overly high in vitamin A, which includes vitamin supplements containing vitamin A or beta-carotene and liver-

based food or liver oil products for the most part. Consumption of fruits and vegetables is not restricted. See section [1.11.2](#) for details.

## **1.8 SUBJECT SELECTION**

### **1.8.1 Inclusion Criteria**

A prospective subject will be eligible if he/she meets **all** the following inclusion criteria at screening or at randomization (as applicable), except upon sponsor's approval which shall be documented:

*General inclusion criteria:*

1. Male or female 60 years and older.
2. Healthy as judged by investigator.
3. Has signed and dated the informed consent form.
4. Is able and willing to perform the study procedures.
5. Is able and willing to comply with the schedule of the study visits.
6. Is able and willing to self-administer the study drug.
7. Is able and willing to follow the instructions and comply with the avoidance of vitamin A supplements.
8. Is likely to complete the 2-year study as judged by the investigator.

*At least one eye, designated as the “study eye”, must meet all the following inclusion criteria:*

9. Study eye displays well-demarcated GA lesion(s) measuring a total area between approximately 1.5 sqmm and 20 sqmm, measured on fundus autofluorescence imaging (FAF), as confirmed by sponsor or designee.
10. Study eye presents hyperautofluorescent borders in the junctional zone of GA, as confirmed by sponsor or designee.
11. If GA lesions are multifocal in the study eye, one lesion at least must be approximately 1.00 sqmm or greater.
12. In case of foveal sparing, the smallest distance between GA border and foveal center must be under approx. 250 µm.
13. All GA lesions in the study eye must fit entirely within the 30-degree retinal imaging field centered on fovea.
14. Study eye has ETDRS BCVA of 33 letters (~20/200) or better.
15. Study eye has clear or adequate ocular media and pupillary dilation, including no allergy to dilating eyedrops, to permit good quality retinal imaging as judged by the investigator.

*The non-study eye, designated as the “fellow eye”, must meet all of the following inclusion criteria:*

16. Fellow eye presents with one of the following features: (a) reticular pseudodrusen (RPD), (b) intermediate AMD with at least one macular drusen greater than approximately 125 µm in diameter, (c) active or history of CNV, (d) geographic atrophy with or without a history of, or concurrent CNV.

### **1.8.2 Exclusion Criteria**

A prospective subject will **not** be eligible if **any** of the following criteria apply at screening or at randomization (as applicable), except upon sponsor's approval, which shall be documented:

*General exclusion criteria:*

17. Active or historical medical condition (systemic or ophthalmic), which in the opinion of the investigator, may prevent performance of study procedures, compliance with the protocol, or continuous participation of the subject throughout the 2-year duration of study.
18. Currently taking or has taken medications associated with retinal toxicity, except for short durations as judged by investigator.
19. Is currently taking oral retinoids or medications that might affect absorption, metabolism, or function of vitamin A.
20. Has participated in any drug or device trial within 60 days of randomization.
21. Anticipates participating in any other drug or device trial over the next 2 years.
22. Is hypersensitive or allergic to fluorescein.
23. Has clinically-significant abnormal laboratory result(s) at screening, which in the opinion of the investigator, makes the patient unsuitable for study participation.
24. Has clinically-significant abnormal physical exam finding(s) at screening, which in the opinion of the investigator, makes the patient unsuitable for study participation.
25. Has active or historical, acute or chronic, liver disorder except when benign.
26. Has a clinically-significant cardiac abnormality, a clinically-significant abnormal ECG, or a marked prolongation of QTc at screening (>460 msec for male or >480 msec for female, approximately).
27. Female of childbearing potential, pregnant, lactating or positive serum pregnancy test at screening.

*Study eye exclusion criteria:*

28. Study eye has historical or active CNV.
29. Study eye has myopia of -6 diopters or more approximately, except if retinal imaging can be properly focused.
30. Study eye has GA thought or proven to be caused by any condition other than AMD.
31. Study eye has GA lesions expected to (i) expand larger than the imaging field of view, or (ii) merge with other retinal features (optic disc or peripapillary atrophy, other non-AMD atrophic lesions, etc.) during the 2 years of the study.
32. Subject, in the case of a systemic treatment, or study eye, in the case of a monocular treatment, has previously received treatment, surgery or procedure for GA or AMD, including clinical trials, except when there is documented evidence that the subject was receiving placebo or was part of a sham group.
33. Study eye has active or history of ocular disorder, which may confound assessment of the retina morphologically or functionally, as judged by investigator.
34. Study eye has active or history of glaucoma, uncontrolled elevated intraocular pressure, retinal detachment, RPE tear, recurring uveitis, retinal vein occlusion, diabetic retinopathy, diabetic macular edema.
35. Study eye has history of submacular or intraocular surgery, vitrectomy, or device implantation (except IOL).
36. Study eye has received intravitreal injections or cataract surgery within 90 days of randomization.
37. Study eye is expected to require cataract, epiretinal membrane, or ocular surgery over the next 2 years as judged by investigator.

**NOTE:** PI shall make the final determination regarding all eligibility criteria.

### **1.8.3 Study Requirements, Restrictions and Instructions for Subjects**

Investigator should enroll participants they believe will follow the study requirements and be likely to complete the 24-month treatment period. Investigators shall discuss with prospective and enrolled subjects about the importance of the study requirements outlined below. Subjects must be willing and able to continuously adhere to the study requirements throughout the duration of the study. Non-compliant subjects will be withdrawn from the study and have to discontinue the study treatment. Details about each of the below requirement are found in the corresponding section.

1. **Adherence to visit schedule:** subjects will be informed about the schedule of all future visits and should ensure they have the time to participate in the 24-month study, and the resources to travel to/from the sites. Missed visit may result in withdrawal.
2. **Study procedures:** subjects should be informed of which study procedures will be performed.
3. **Compliance with study drug intake:** subjects should be informed before the study, and reminded during the study, to take the drug daily for 24 months, preferably at the same time every day and at the same time they take their other medications, unless prescribed otherwise by the investigator.
4. **Subjects must not consume dietary supplements containing vitamin A, liver-based products, or foods known to contain excessive amounts of vitamin A** (section 1.11.2).
5. **Subjects should not take any medications prohibited under this protocol**, except when medically indicated, for the duration of the study (section 1.11.3).
6. **Subjects must not enter into any other investigational drug or device clinical study**, unless deemed medically necessary by the PI and sponsor.

### **1.8.4 Exemptions to Entry Criteria**

Subjects must be compliant with all inclusion and exclusion criteria, unless explicitly permitted in writing by sponsor. Such deviation should only be permitted if it would not be of clinical or scientific significance and would have no significant effect on the results of the study. The exemption should be documented in the source documents and correspondence (including oral notes) recorded in the regulatory binder.

## **1.9 STUDY DRUG ADMINISTRATION AND MANAGEMENT**

### **1.9.1 Treatment Groups**

Subjects will be considered “enrolled” when they are determined to have met all eligibility criteria **and** after they are randomized to a treatment group. Subjects will be randomized 2:1 to 14 mg/day of ALK-001 or placebo. The treatment period will last for up to 24 months and subjects and investigator will be masked to treatment group.

### 1.9.2 Timing of study drug intake

- a) Subjects will be instructed to take one capsule per day, by mouth, at a time of the subject's preference, usually at the same time they take their other daily medications.
- b) Subjects will be instructed to take the study drug at approximately the same time each day.
- c) Time of usual study drug intake, duration elapsed since last study drug intake (at the time blood samples are collected during follow-up visits), and whether the capsule is taken before, after or during a meal should be recorded.
- d) If subjects are taking their study drug in the morning, subjects should not take a dose on the morning of a follow-up visit. Instead, they should wait until after blood collection is completed for that visit to take that day's dose.

### 1.9.3 Missed Dose

- a) Subjects should avoid missed doses.
- b) If a subject forgets to take a dose, they should take the missed dose as soon as they remember it, even if that means taking 2 doses on the same day.
- c) Subjects should not take more than 2 capsules in one day.

### 1.9.4 Method of Assigning Subjects to Treatment Groups

Randomization: Only after receiving authorization to do so by the sponsor, investigator will randomize subjects who are confirmed to meet all entry criteria at screening and continue to meet those criteria on day of randomization. Randomization consists in assigning a medication ID to a subject and to dispense the study medication, usually at the same time. Subjects are allocated a treatment based on random, permuted block sizes. Blocks are randomly selected from a size of 3 or 6.

Errors in Medication ID assignment: If a subject is assigned a medication ID in error and has not started treatment, the error shall immediately be corrected and documented, so that the subject receives the medication he/she was supposed to receive.

If a subject has already been dispensed and has already taken one capsule of the wrong medication ID, the drug dispensed medication ID shall now prevail and should replace the medication ID originally intended to be dispensed. However, no two subjects shall be assigned the same medication ID, and if a dispensing error has been made, the subject receiving the wrong medication shall be informed to immediately stop taking the wrongly provided medication, to return all provided medication, and to start receiving the proper medication. Randomization date shall be adjusted to the date at which the subject started the proper medication. A note should be added to the source documents to explain the discrepancy.

Process: A randomization list is used to identify which medication ID to dispense to the subject about to be randomized. The investigator must pick the next medication ID available at the clinical site, by following the order on the masked randomization list which will be distributed to the investigator at the start of the trial. The sponsor will be responsible for shipping out drug supplies to each site. To ensure proper drug supply is at each site, investigators should inform the sponsor in advance of subjects' scheduled randomization visits, so that sufficient drug supply is already at

the site on the scheduled day of the patients' randomization visit. An online randomization portal may also be used, in place of the paper randomization list.

Once randomized, subjects will immediately receive their first study medication bottle either through the PI or designated personnel, through the site pharmacy, or directly by mail. If received by mail, subjects will be requested to confirm receipt, which shall be documented.

Randomization code, randomization list (or schedule): A randomization code, used to prepare the randomization list, will first be prepared by the sponsor. The code will be programmed so as to be reproducible if the need arises. Once approved, this code will be tested by the sponsor to generate a dummy randomization list for quality control. Once the code has been verified to work properly, an unmasked vendor/consultant designated by the sponsor will generate the final randomization lists (masked and unmasked). The unmasked randomization list will be accessible to select persons only (SMC members, unmasked statistician(s), label printing company, packaging company, other unmasked vendors). The investigator and the sponsor will receive a copy of the masked randomization list which will contain the sequence of medication IDs, but not the actual treatment allocation nor any information about blocks order or size. Any further instructions for randomization will be provided separately.

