### **1.5.1 Definitions: Investigator; PI; Sponsor**

In this document, “investigator” or “study team” shall designate indifferently the entire clinical team, including the principal investigator (PI), sub-investigator(s), and the clinical research team (research coordinators, ophthalmic technicians, etc.) of each site participating in the study.

“Principal Investigator” or “PI” shall designate only the PI, i.e. the person signing form 1572. PI is responsible for the overall conduct of the clinical trial at his/her institution, and for the supervision and

oversight of adequately qualified and trained personnel who have been delegated protocol-related activities.

“Sponsor” shall designate the study sponsor, Alkeus Pharmaceuticals, and its affiliates or other representatives (including for example contract research organizations or other organizations acting on behalf of the sponsor).

“Study drug”, “study medication” and “study treatment” shall be synonymous and designate the investigational treatment (drug or placebo) provided to study subjects.

Study “Subjects” or “participants” shall designate individuals who participate in the present study.

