#### 1.9.4.2 Errors in Medication ID assignment

If a subject is assigned a medication ID in error (except for placebo during run-in period and has not started treatment, the error shall immediately be corrected and documented, so that the subject receives the medication he/she was supposed to receive.

If a subject has already been dispensed and has already taken one capsule of the wrong medication ID, the drug dispensed medication ID shall now prevail and should replace the medication ID originally intended to be dispensed.

No two subjects shall be assigned the same medication ID (except during run-in period, and if such dispensing error has been made, the subject receiving the wrong medication shall be informed to immediately stop taking the wrongly provided medication, return all provided medication, and start receiving the proper medication. Randomization date shall be adjusted to the date at which the subject started the proper medication. A note should be added to the source documents to explain the discrepancy. If this dispensing error results in insufficient study drug available for a given subject, refer to section [1.9.8.2](#).

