#### 1.9.8.3 *Lapse in treatment*

If a lapse in treatment occurs, the days and duration that subject was off-treatment shall be documented. If the subject is off-treatment for a period longer than 4 weeks, and if subject lives relatively close to study site, study team may collect subject's plasma in an unscheduled visit to acquire pharmacokinetic data caused by lapse in treatment.

Lapse in treatment may occur for a variety of reasons, including health-related reason, temporary interruption, lost medication, subject forgetting to take treatment, study drug availability, family or personal reason, etc.

Lapse in treatment shall not result in modifications or postponing of subsequent follow-up visits, unless instructed by sponsor. Lapse in treatment may result in early withdrawal.

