## 1.16 ADVERSE EVENTS

### 1.16.1 Definition of Adverse Events

**Definition.** An adverse event (AE) or “Treatment Emergent Adverse Event” (TEAE) is defined as any untoward medical occurrence in a subject that occurs after randomization (V02) or due to the performance of a protocol-specific procedure or assessment, *whether or not it is caused by the study drug*. Medical occurrences that occur prior to V02 or are not due to protocol-specific procedure or assessment will be considered part of medical history.

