4.2. Reference Start Date and Study Day

Reference start date is defined as the date of the first study drug administration following the end of the run-in period, which is designated as Day 1, and the preceding day is Day -1, etc.

Study day will be calculated from the reference start date and will be used to show the start/end day of assessments or events.

Study day will be computed as follows:

- Study Day = Assessment/event date – reference start date + 1 if the assessment/event date is on or after the reference start date.
- Study Day = Assessment/event date – reference start date if the assessment/event date is before the reference start date.

In the situation where the assessment/event date is partial or missing, study day and any corresponding duration will appear as partial or missing in the listings.

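### After a duplicate-ID dispensing error the protocol moves the randomization date, which separates its Day 1 from the SAP's and lets a site file events on the wrong medication as medical history

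*Protocol*

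**What the plan says.** The rule stands in both protocol versions in identical words: "Randomization date shall be adjusted to the date at which the subject started the proper medication". In v1.1 (section 1.9.4.2), the version on which the SAP is based, the trigger is a duplicate ID: "No two subjects shall be assigned the same medication ID (except during run-in period, and if such dispensing error has been made" (the bracket is not closed in the source). The subject is told to stop the wrongly provided medication and start the proper one. For any other wrong ID from which a capsule has already been taken, the same section keeps the medication and moves no date: "the drug dispensed medication ID shall now prevail and should replace the medication ID originally intended to be dispensed".

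The dates that depend on this are:

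- **Protocol v1.1, 1.13.2:** the randomization visit V02 is Day 1.
- **Protocol v1.1, 1.16.1:** an adverse event is "any untoward medical occurrence in a subject that occurs after randomization (V02") or one due to a protocol procedure. The next sentence reads "Medical occurrences that occur prior to V02 or are not due to protocol-specific procedure or assessment will be considered part of medical history".
- **SAP 4.2:** "Reference start date is defined as the date of the first study drug administration following the end of the run-in period", and that date is Day 1. SAP 7.2 uses it for treatment-emergent events and SAP 4.7 for exposure.

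For other interruptions of dosing, Protocol v1.1 section 1.9.8.3 leaves the calendar alone: "Lapse in treatment shall not result in modifications or postponing of subsequent follow-up visits, unless instructed by sponsor".

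**The concern.** Randomization is an event that happened on a known day. Version 1.1 section 1.9.4.1 describes it as assigning a medication ID and dispensing drug, and both have taken place before the error is found. Section 1.5.1 defines study drug so as to "designate the investigational treatment (drug or placebo) provided to study subjects", so capsules from the wrong bottle are study drug taken after run-in. Moving the date forward places that exposure before the subject's recorded randomization.

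Three things are at stake for such a subject: whether events on the wrong medication are collected as adverse events, whether the two documents agree on study day, and whether follow-up visits keep their intended distance from baseline.

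**Working it through.** The plan gives no figure to reproduce. The check compares the date anchors and works out the offset between the two calendars.

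**Offset.** Let k be the number of days from the first wrong capsule to the first proper capsule. SAP Day 1 is the first wrong capsule; protocol Day 1, after adjustment, is the first proper capsule. Hence

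SAP study day = protocol day + k.

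The documents do not give k. I assume a range of 7 to 90 days for illustration.

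**Adverse events.** Take an event on day j of wrong-medication use, with 1 ≤ j ≤ k.

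- Under the SAP it is study day j, on or after the reference start date, so it is treatment-emergent if the site recorded it as an adverse event.
- Under v1.1 section 1.16.1 read with the moved date, it precedes randomization and may be medical history. Section 1.15.7.1 likewise speaks of a dose after randomization.
- Under v1.1 section 1.16.1.4, and the history sentence of 1.15.7.1, the anchor is the first administration of study drug, which points back to an adverse event.

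Version 1.1 therefore carries two anchors. They normally coincide, and the date adjustment pulls them apart.

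**Study day and visit windows.** SAP 4.4 (Table 1) splits Month 6 from Month 12 at study days 270/271 for unscheduled and early-termination visits. On the protocol's adjusted calendar that boundary lies at:

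- k = 7: 270 − 7 = 263 and 271 − 7 = 264
- k = 90: 270 − 90 = 180 and 271 − 90 = 181

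**Exposure.** SAP 4.7 counts from the reference start date, so it is k days longer than a count from the moved date.

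**Interval to Month 24.** SAP 4.3 takes as baseline the last value before first study drug, so baseline does not move. If visits were re-timed from the adjusted date, a visit on protocol day 720 (the Month 24 target in Table 1) would be SAP study day 720 + 7 = 727 or 720 + 90 = 810. No section says that visits follow the adjusted date. Nor does any section exclude it, because visit targets are counted from Day 1 and protocol Day 1 is randomization.

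**The case against.** The case against is substantial.

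- V02 is a visit that has already taken place when the wrong bottle is in use, and the rule changes a date, not a visit. Sections 1.12.17 and 1.12.18 of v1.1 confine medical history to findings between V01 and V02, and 1.16.1.4 uses first study drug. In v1.0 the reporting period starts at the first study dose (1.16.1.12). On this reading no event is lost.
- The sentence after the rule requires a source-document note, and v1.1 section 1.17.11 requires every deviation to be documented.
- The SAP supersedes the protocol's statistical sections, has one Day 1, uses nominal visits for by-visit summaries (4.4), counts wrong-bottle days as exposure (4.7), and names dispensing of incorrect drug among its examples of major deviations for the Per Protocol Set (4.5).

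Most of this stands, and it limits the size of the problem. A reader might infer that the rule hides exposure to the other arm's drug; for the reasons in the last two bullets, the documents do not support that.

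It does not remove the problem. The SAP's precedence covers endpoints, power and analysis, whereas adverse event collection is set in Protocol section 1.16. The SAP can count only what a site recorded as an adverse event, and the definition a site would consult in v1.1 refers to randomization. No section reconciles the moved date with the reference start date.

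**Conclusion.** The point holds as a defect in a stated rule, narrow in reach. In v1.1, a duplicate-ID error followed by the date adjustment makes it possible, not certain, that events on the wrong medication are filed as history at the site. It also makes protocol Day 1 and SAP Day 1 differ by k days, and it leaves open a re-timing of visits that section 1.9.8.3 rules out for lapses unless the sponsor instructs it. The medical-history consequence does not follow directly under v1.0.

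A reader might go further and infer an inflated growth rate by scaling the assumed 1.8 mm²/year by (24 + added months)/24. The documents do not support a figure of that kind. No section expressly re-times visits. The scaling is a two-point calculation, whereas SAP 6.1.3 fits a slope with continuous time and does not say whether time is nominal or actual; with actual time the delay would be in the model. The duration of the error is not given. Nor can the chance that the wrong bottle came from the other arm be read off the 2:1 ratio, because assignment is in blocks of 3 or 6 (SAP 3.1).

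The error is rare, the number of affected subjects is not reported, and no effect on the primary result can be quantified. The 7-to-90-day range is an assumption. The point is worth correcting because the rule is wrong whenever it applies and the correction is nearly free.

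**What to change.** 1. Delete the date-adjustment sentence. Keep the original randomization date and use one Day 1 in both documents: the first post-run-in capsule, as in SAP 4.2.
2. Record the wrong ID with its start and stop dates, as a deviation and as exposure. The dates are also needed because the Safety Set (SAP 4.5) is analysed by actual treatment received and has no rule for a subject who took both treatments.
3. State that adverse events are collected from the first post-run-in capsule, whichever ID was dispensed, and that visits stay on the original schedule.
4. SAP 3.1 reports 200 subjects already randomized, so the practical step is a data check before database lock. Search for any subject with an adjusted randomization date, restore the original, and review events recorded as medical history during wrong-bottle use. Medication IDs and dates are enough for this, so masking is unaffected.

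The cost is one deleted sentence, a clarification and a short listing review. No new data are needed. How the dispensing error should be handled clinically is not addressed here.
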